5.2.6. Long Term Follow-up/ Day 90 (+ 14 days)

The following procedures and assessments will be performed and documented.

- SSC Assessment
- Intervention Assessment
- PRO assessments (KOOS and PROMIS Global-10)
- Healthcare Utilization Assessment
- Concomitant Medications
- AE Assessment and SAE Reporting
- End of Study

5.2.7. Unscheduled Visits

Outside of scheduled study visits, if the subject needs to be assessed by the Investigator for any reason, the following procedures and assessments will be performed and documented.

- SSC Assessment
- Intervention Assessment
- Healthcare Utilization Assessment
- Concomitant Medications
- AE Assessment and SAE Reporting
- End of Study (only when a subject discontinues prior to the 90-day visit)

6. RISKS ASSOCIATED WITH STUDY PARTICIPATION

The following are the risks associated with the devices and dressings used in this study, specifically, ActiV.A.C.® Therapy Unit, Prevena Plus™ 125 Therapy Unit, and Prevena™ Dressings.

Risks	Disorders/Conditions
Skin and Subcutaneous Tissue	
 • Epidermal (skin) stripping. • Contusion (bruising) • Local cutaneous reaction (i.e., redness, rash, significant pruritis, urticaria) • Maceration • Minor soft tissue damage • Minor bleeding • Pain
Other	
 • Allergic reaction • Bleeding complications (associated with the surgical procedure, concomitant therapies and co-morbidities) • Increased risk of bleeding from the incision associated with the use of anticoagulants and/or platelet aggregation inhibitors • Deterioration of the wound (due to lack of visibility of incision site through dressing) • Exposure related infection • First degree burn (if device gets warm) • Localized infection • Minor desiccation (due to dressing leak) • Moderate soft tissue damage (i.e., due to trip hazard, tubing entanglement) • Physical discomfort • Surgical Site disruption

7. SAFETY AND ADVERSE EVENTS

7.1. Definitions

7.1.1. Adverse Event (AE)

Any untoward medical occurrence, unintended disease or injury, or untoward clinical signs (including clinically significant abnormal laboratory findings) in subjects, users or other persons, whether or not related to the investigational medical device.

[figure not shown]
7.1.2. Serious Adverse Event (SAE)

An AE is considered serious if it results in any of the following outcomes:

- Death;
- Life-threatening;
- Hospitalization (initial or prolonged);
- Persistent or significant incapacity or substantial disruption of the ability to conduct normal life functions
- Congenital anomaly/birth defect;
- Required intervention to prevent permanent impairment or damage
- Other important medical events may be considered serious when, based upon appropriate medical judgment, they may jeopardize the subject and may require medical or surgical intervention to prevent one of the outcomes listed in this definition.

Any planned hospitalization for a pre-existing condition, or a procedure required by the protocol, without serious deterioration in health, is not considered an SAE.

7.2. Classification

7.3. Relationship to Study Treatment

The Investigator will assess the relationship of the AE as:

- **Related** to the study product: any adverse event for which there is a reasonable possibility that the study product caused the adverse event.
- **Not Related** to the study product: when is determined that there is no relationship between the adverse event and the use of the study product.

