Protocol

Post-market, Randomized, Open-Label, Multicenter, Study to Evaluate the Effectiveness of Closed Incision Negative Pressure Therapy versus Standard of Care Dressings in Reducing Surgical Site Complications in Subjects with Revision of a Failed Total Knee Arthroplasty (PROMISES)

NCT Number

NCT03274466

Document Date

06-OCT-2018

An Acelity Company

Post-market, Randomized, Open-Label, Multicenter, Study to Evaluate the Effectiveness of Closed Incision Negative Pressure Therapy versus Standard of Care Dressings in Reducing Surgical Site Complications in Subjects with Revision of a Failed Total Knee Arthroplasty (PROMISES)	
PROTOCOL NUMBER	KCI.PREVENA.2017.01
SPONSOR	KCI USA, Inc. [name] [contact]
STUDY PRODUCTS	ActiV.A.C. [®] Therapy Unit or Prevena Plus™ 125 Therapy Unit in combination with Prevena™ Incision Dressing
ORIGINAL PROTOCOL VERSION/DATE	Version 3.0, 6-Oct-18

Confidentiality Statement: This document is a confidential communication of KCI, an Acelity Company. Acceptance of this document constitutes the agreement by the recipient that no unpublished information contained herein will be published or disclosed without the prior written approval of KCI. This document may be disclosed to appropriate Institutional Review Boards (IRBs) so long as they are requested to maintain its confidentiality.

TITLE:	Post-market, Randomized, Open-Label, Multicenter, Study to Evaluate the Effectiveness of Closed Incision Negative Pressure Therapy versus Standard of Care Dressings in Reducing Surgical Site Complications in Subjects with Revision of a Failed Total Knee Arthroplasty (PROMISES)
PROTOCOL NUMBER:	KCI.PREVENA.2017.01
TYPE AND PHASE:	Post-market, prospective, randomized, open-label
STUDY PRODUCT(S):	ActiV.A.C. [®] Therapy Unit or Prevena Plus [™] 125 Therapy Unit and Prevena [™] Dressing
STUDY OBJECTIVE(S) :	The goal of this study is to evaluate surgical site complications (SSCs) in subjects undergoing a revision of a failed total knee arthroplasty (TKA) when closed incision negative pressure therapy (ciNPT) is used to manage the closed incision, as compared to standard of care dressing.

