1.5. Study Products

The following devices and dressings will provide the ciNPT system used for this study in comparison to standard of care (SOC) surgical dressings. The system consists of any United States Food and Drug Administration (FDA)-cleared Prevena™ Incision Management System dressing, including but not limited to:

- Prevena™ Peel & Place™ Dressings (section 1.5.3), or
- Prevena Plus™ Customizable™ Dressing (section 1.5.4)

applied at the time of the surgery and one of the following negative pressure pumps:

- ActiV.A.C.® Therapy Unit (section 1.5.2.1), or
- Prevena Plus™ 125 Therapy Unit (section 1.5.2.2).

The products provide surgical incision management via the application of negative pressure wound therapy over an incision site that has been surgically closed with sutures or staples.

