7.10. Follow-up Period for Ongoing AEs

Treatment-related AEs (serious and non-serious) which are ongoing at the final study visit will be followed until resolution or stabilization. All other adverse events will be considered closed (outcome = “ongoing”) at the time the subject completes participation in the study.

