9.1 Adverse Events

All treatment-emergent adverse events (TEAEs), which are defined as adverse events with onset or worsening of pre-existing condition on or after the initial dressing application through the course of the study, will be summarized. Number and percentage of treated subjects who experienced at least one adverse event in each system organ class by preferred term will be summarized. In any given category (e.g., system organ class or preferred term) a subject will be counted only once. The denominator for the calculation of percentages will be the number of subjects in the Safety analysis set.

The following summary tables and listings will be presented by treatment arm:

- Overview of all treatment-emergent adverse events (TEAEs)
- Incidence of all treatment-emergent adverse events (TEAEs) by system organ class and preferred term
- Incidence of all treatment-emergent adverse events (TEAEs) by system organ class, preferred term, and maximum severity
- Incidence of all serious adverse events (SAEs) by system organ class and preferred term
- Incidence of treatment-related TEAEs by system organ class and preferred term
- Incidence of treatment-related TEAEs by system organ class, preferred term, and maximum severity
- Incidence of treatment-related serious adverse events (SAEs) by system organ class and preferred term
- Listing of all treatment-related adverse events
- Listing of all treatment-related serious adverse events (SAEs)
- Listing of discontinuations: Subjects who discontinued from the study due to any adverse event
- Listing of deaths: Subjects who died of any cause during the study

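### Protocol 7.3 defines AE relatedness against the study product (ciNPT only), while the rules and tables that use it refer to study treatment (both arms), so related-event counts can differ by arm or site for reasons of wording

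*Protocol*

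**What the plan says.** Protocol 7.3 is the only place in either document that tells an investigator how to judge relatedness. Its heading is "Relationship to Study Treatment". Its two categories use another term:

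- Related: "any adverse event for which there is a reasonable possibility that the study product caused the adverse event".
- Not Related: "when is determined that there is no relationship between the adverse event and the use of the study product".

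The title page lists the study products as the ActiV.A.C. unit or the "Prevena Plus™ 125 Therapy Unit in combination with Prevena™ Incision Dressing". Section 1.5, headed Study Products, says: "The following devices and dressings will provide the ciNPT system used for this study in comparison to standard of care (SOC) surgical dressings". In both places the SOC dressing is absent or named as the comparator.

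The sections that use the judgment are worded differently:

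- Protocol 7.7 asks for the relationship to study treatment in the AE record. It uses the same term to decide which SAEs are reported after alternative therapy. It also says that AEs are recorded whatever their perceived relation to the study product.
- Protocol 7.10 follows treatment-related AEs beyond the final visit. For the rest: "All other adverse events will be considered closed".
- Protocol 8.3.7 summarizes AEs and SAEs related to treatment, by arm.
- SAP 9.1 lists, among its by-arm outputs, "Incidence of treatment-related TEAEs by system organ class and preferred term".

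**The concern.** The two terms do not cover the same things. Study product is the ciNPT system. Study treatment covers both arms: Protocol 4.10.2 has a ciNPT and an SOC subsection under that name, and the Safety Analysis Set assigns subjects by the study treatment they received.

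An investigator who applies the 7.3 definitions as worded can therefore call a skin reaction under the SOC dressing Not Related and the same reaction under a Prevena dressing Related. The trial is open-label, so the arm is always known when this judgment is made. Two things are at stake:

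- **Tables.** Five of the eleven outputs in SAP 9.1 (three tables and two listings) depend on relatedness. SAP section 9 also allows descriptive between-arm p-values on safety.
- **Reporting and follow-up rules.** A reaction still ongoing at the last visit could be followed in the ciNPT arm and closed in the SOC arm. The 7.7 rule on SAEs after alternative therapy could also be applied differently by arm.

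**Working it through.** The documents state no figure on this point, so there is nothing to reproduce. The first check is textual.

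| Place | Term used | Arms covered |
|---|---|---|
| Protocol title page, 1.5 | study product | ciNPT only |
| Protocol 7.3, heading | study treatment | both |
| Protocol 7.3, both definitions | study product | ciNPT only |
| Protocol 7.7, AE record and SAE rule | study treatment | both |
| Protocol 7.7, recording of all AEs | study product | ciNPT only |
| Protocol 7.10 | treatment-related | both, if read as study treatment |
| Protocol 8.3.7 | related to treatment | both, if read as study treatment |
| SAP 9.1 | treatment-related | both, if read as study treatment |

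No section equates treatment-related with related to the study product, and none says how to attribute a reaction to the SOC dressing. Protocol section 6 lists risks for the ciNPT units and dressings only, so it does not help.

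The second check is an illustration of size.

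- **From the documents:** about 440 subjects at 1:1 (Protocol 3.2), so 440/2 = 220 per arm.
- **Assumptions:** a true rate *r* of dressing-caused reactions that is the same in both arms (the documents give none, so a range is shown), and every SOC case coded Not Related.
- **Expected recorded related cases:** 220 × *r* for ciNPT and 0 for SOC.
- **Fisher's exact test, two-sided, *k* of 220 against 0 of 220:** p = 0.12 for *k* = 4, 0.061 for *k* = 5, 0.030 for *k* = 6 and 0.0009 for *k* = 11. Six or more against none therefore falls below 0.05.
- **Chance of a spurious p < 0.05:** P(X ≥ 6) with X binomial(220, *r*).

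| Assumed rate in both arms | Expected related cases, ciNPT vs SOC | Chance of spurious p < 0.05 |
|---|---|---|
| 1% | 2.2 vs 0 | about 2% |
| 2% | 4.4 vs 0 | about 28% |
| 5% | 11 vs 0 | about 97% |
| 10% | 22 vs 0 | over 99.9% |

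If only a fraction *f* of SOC cases is coded literally, the apparent difference in rates is *f* × *r*. For example, *r* = 5% and *f* = 0.5 gives 11 against 220 × 0.05 × 0.5 = 5.5 expected cases, a gap of 2.5 percentage points. At *f* = 0, which is the study-treatment reading, the gap is nil.

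**The case against.** The strongest answer is that the documents do not compel the literal reading. The heading of 7.3, the AE record in 7.7, the follow-up rule in 7.10 and the safety tables all speak of treatment, and study treatment includes SOC. An investigator following 7.7 could properly record an SOC dressing reaction as related. Presenting the related-event tables by arm also fits relatedness being possible in both arms. What sites actually record depends on the eCRF and its completion guidance, which are not in the documents.

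This stands, and it rules out the stronger readings. A reader might infer that SOC reactions must be coded Not Related, that the SOC column is zero by construction, or that the tables will show a false gap of a particular size. The documents support none of these. Any gap in percentage points only restates an assumed reaction rate combined with an assumed coding habit.

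It is also fair that the consequences are limited. The safety endpoint is AE incidence regardless of cause. All-causality TEAE and SAE tables by arm do not use 7.3, and any p-values on safety are optional and exploratory. The follow-up difference arises only for a reaction still ongoing at the final visit, at day 90 to 104, and the documents give no reason to expect many. Finally, judging relatedness to the sponsor's own device has a purpose, because UADEs must be reported.

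The objection does not remove the conflict. The only operational definitions name the study product, and 7.7 itself uses both terms. If sites can properly read the text two ways, the related-event counts depend on which reading each of about 15 sites adopts, and the pooled by-arm comparison has no single meaning.

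**Conclusion.** The point holds as an unreconciled conflict of terms. On a literal reading of 7.3, the treatment-related AE and SAE tables can be biased against ciNPT. On mixed readings they can vary by site. The rules in 7.7 and 7.10 can be applied unequally by arm.

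The size cannot be determined from the documents. The range of about 2 to 22 expected related cases against 0 rests on 220 subjects per arm, an assumed equal true rate of 1% to 10%, and fully literal coding. The distortion shrinks in proportion as fewer SOC cases are coded that way. The efficacy endpoints and the all-causality safety results are not affected.

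**What to change.** - In Protocol 7.3, define Related and Not Related against the study treatment the subject received, stated as the ciNPT system or the SOC dressing.
- Bring Protocol 7.7, 7.10, 8.3.7 and SAP 9.1 to that single term, so that the same question is asked in both arms and drives both the tables and the follow-up rules.
- Record relatedness to the Prevena system as a separate item for UADE and other device reporting, and keep it out of the by-arm comparison.

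The cost is one revised definition with matching edits, one more eCRF item, and follow-up of related events in the SOC arm on the same terms as in the ciNPT arm.

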7.4. Severity

The study investigator will assign severity as follows:

- **Mild**; asymptomatic or mild symptoms; clinical or diagnostic observations only; no intervention indicated
- **Moderate**; minimal, local or non-invasive intervention indicated;
- **Severe** or medically significant but not immediately life-threatening; hospitalization or prolongation of hospitalization indicated; disabling;

7.5. Expectedness

All SAEs will be classified for expectedness by the Sponsor based on the following definitions:

- **Expected, Anticipated**: the effect, problem, or death has been previously identified in the study or product documentation.

- **Unexpected, Unanticipated:** if that effect, problem, or death was not previously identified in nature, severity, or degree of incidence in the study or product documentation.

The Sponsor will provide the Investigator with the classification of the event based on the information reported by clinical sites.

7.6. AE Reporting Procedures

The Investigator is responsible for monitoring the safety of all subjects enrolled in the study, and reporting AEs as described in this protocol.

7.7. AE Collection/Reporting Period

The AE collection/reporting period will begin after the subject has been randomized. Investigators should assess for AEs at each visit. In addition, study subjects should be instructed to report any AE that they experience to the Investigator.

All AEs, regardless of perceived relationship to study product, will be reported and recorded on the appropriate CRFs in a timely manner. In addition, the worsening of a medical condition previously reported in the medical history should also be recorded as an AE.

The reporting of all AEs is to continue for the duration of the study or until the patient receives an alternative therapy, whichever occurs first. Any SAE that occurs after treatment with alternative therapy is to be reported only if the Investigator or treating physician assesses the SAE as related to the study treatment.

The AE description will include the nature of the experience (AE term), the start date, the end date, the severity of each sign or symptom, the seriousness of the event or experience, relationship to study treatment, the course of action taken, and the outcome of the experience. Indicate if the AE caused the subject to be discontinued from the study.

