3.2. Design Summary

This post-market, prospective, randomized, open-label, multicenter, controlled study will evaluate the effectiveness of closed incision negative pressure therapy (ciNPT) compared to standard of care (SOC) surgical dressing in reducing the surgical site complications (SSCs) in subjects with revision of a failed total knee arthroplasty (TKA).

The study will randomize approximately 440 subjects from approximately 15 sites in a 1:1 ratio to receive either ciNPT or SOC after a revision TKA. Subjects randomized to the ciNPT treatment arm will receive the placement of a Prevena™ Dressing in conjunction with ActiV.A.C.® or Prevena Plus™ 125 Therapy Units for a duration consistent with the Instructions for Use (IFU) document for the selected dressing but no shorter than five days post-surgery. Subjects randomized to the SOC treatment arm will receive Aquacel® Ag Surgical incision dressing, or another equivalent silver-impregnated dressing, up to the maximum number of days specified in the IFU but no shorter than five days post-surgery, not inclusive of other negative pressure wound therapy devices or dressings for the duration of the study.

Subjects will be seen during Screening (no more than 30 days before TKA revision) at the TKA revision, at weekly study treatment visits (a minimum of 5 days to a maximum number of days indicated in the Instruction for Use document for the selected dressing), the Midterm Follow-up visit (day 30 to 45), the Long Term Follow-up visit (day 90 to 104), or as initiated by either the Investigator or the subject (Unscheduled). All subjects will be followed for 90 days for outcomes regardless of the treatment received.

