3.7. Safety Endpoint

The safety endpoint is the subject incidence of adverse events.

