4.10.3.3. Documentation

The following information regarding the application of study treatments will be documented after the surgery:

- Date of removal
- SOC only
- The number of dressing replacements
- Type of dressing (if any) applied after removal of study treatment
- ciNPT only
- Replacement of therapy unit
- Number and dates of dressing replacements (Prevena™ Peel & Place™ or Prevena Plus™ Customizable™)
- Type of dressing (if any) applied after removal of ciNPT

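### Protocol 7.7 stops adverse event reporting at an undefined alternative therapy, which contradicts the safety tables and death listing that the SAP promises for the whole study

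*Protocol*

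**What the plan says.** Protocol 7.7 sets the collection period: "The reporting of all AEs is to continue for the duration of the study or until the patient receives an alternative therapy, whichever occurs first". It then narrows the reporting of later serious events: "Any SAE that occurs after treatment with alternative therapy is to be reported only if the Investigator or treating physician assesses the SAE". The condition is a judged link between the event and study treatment. The same section asks for all events to be reported whatever their perceived relationship to the product. Death heads the list of serious outcomes in 7.1.2, so an unrelated death after alternative therapy falls under the related-only restriction.

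Other sections assume complete collection:

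- Protocol 3.7: "The safety endpoint is the subject incidence of adverse events", with no stop at alternative therapy.
- Protocol 3.2: "All subjects will be followed for 90 days for outcomes regardless of the treatment received".
- Protocol 5.1 and 5.2: adverse event assessment and SAE reporting at the treatment, Midterm, Long Term and unscheduled visits, without exception.
- SAP 9.1: treatment-emergent events are those "on or after the initial dressing application through the course of the study", with the Safety Analysis Set as denominator.
- SAP 9.1: "Listing of deaths: Subjects who died of any cause during the study". Protocol 8.3.7 promises the same listing.

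Protocol 4.15 requires withdrawal after cross-over therapy only when there is no SSC. Protocol 4.11.1 keeps subjects with an SSC under assessment through Long Term Follow-up or withdrawal. Alternative therapy appears in Protocol 7.7 and in the modified per-protocol set definition (Protocol 8.2, SAP 5), and is defined in neither document.

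**The concern.** A table of events over the whole study, with every treated subject in the denominator, cannot be built from data that stop earlier for some subjects. The SAP has no censoring rule, exposure adjustment or sensitivity analysis for the cut, and its list of changes in section 10 does not mention it.

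The cut also depends on outcome. The subjects it mainly reaches have had a complication, received something else and are still attending visits. The trial is built on the expectation that complications are twice as common on standard of care, so the loss would differ by arm.

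The exception for serious events does not repair this. It rests on a relatedness judgement made in an open-label trial, and on the literal text it leaves out later non-serious events even when they are related. At stake are the later entries in the preferred-term, SAE and severity tables and the completeness of the death listing.

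**Working it through.** **1. Who is affected.** A subject without an SSC who crosses over leaves the study (4.15), and no further data are collected (4.4.2). A subject with an SSC may receive other therapy and remain (4.15, 4.11.1). For that subject 7.7 ends event reporting while 5.1 and 5.2 still schedule the assessment. This step reads alternative therapy as close to the cross-over therapy of 4.15. If the term is wider, some subjects without an SSC are affected too, which is why the rule acts mainly, not only, on subjects with an SSC.

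**2. The plan's own figures.** The pooled rate on standard of care is 0.5 × 33% + 0.5 × 6.9% = 19.95%, stated as 20%. For 20% vs 10% with two-sided alpha 0.05, power 80% and pooled variance:

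n = [1.960 × √(2 × 0.15 × 0.85) + 0.8416 × √(0.20 × 0.80 + 0.10 × 0.90)]² / 0.10² = 1.4106² / 0.01 ≈ 199 per arm, as stated.

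With 440 randomized 1:1, the design rates give 0.20 × 220 = 44 subjects with an SSC on standard of care and 0.10 × 220 = 22 on ciNPT.

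**3. Event follow-up lost.** Let f be the share of subjects with an SSC who receive alternative therapy and stay in the study, and d the day they receive it. Neither is in the documents; I take f from 25% to 100% and d from 7 to 45.

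Share of 90-day event follow-up lost = SSC rate × f × (90 − d) / 90

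| f | d | Standard of care | ciNPT |
|---|---|---|---|
| 25% | 45 | 0.20 × 0.25 × 45/90 = 2.5% | 0.10 × 0.25 × 45/90 = 1.25% |
| 50% | 14 | 0.20 × 0.50 × 76/90 = 8.4% | 0.10 × 0.50 × 76/90 = 4.2% |
| 100% | 7 | 0.20 × 1.00 × 83/90 = 18.4% | 0.10 × 1.00 × 83/90 = 9.2% |

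If f and d are the same in both arms, the loss on standard of care is always twice that on ciNPT.

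**4. Effect on one preferred term.** Take an event distinct from the SSC, with the same true 90-day incidence P in both arms, a constant hazard h = −ln(1 − P)/90, and no dependence on SSC status. With s the SSC rate:

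Recorded incidence = s × f × (1 − exp(−h × d)) + (1 − s × f) × P

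For P = 10%, f = 50% and d = 14, 1 − exp(−14h) = 1.63%. Standard of care: 0.10 × 1.63% + 0.90 × 10% = 9.2%. ciNPT: 0.05 × 1.63% + 0.95 × 10% = 9.6%. At the extreme (f = 100%, d = 7) the figures are 8.2% and 9.1%. The distortion is modest, and at the design rates it runs against ciNPT. It would be larger for events more likely after an SSC.

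**5. Overall subject incidence.** An adverse event is any untoward medical occurrence (7.1.1), and 4.11.1 treats SSC events as falling among reported adverse events that are surgical complications. The SSC comes before the switch, so it is reported before the cut. Each subject counts once (SAP 9.1). A subject with an SSC is therefore ordinarily already a case, and the later cut does not remove that subject from the overall count.

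**The case against.** The strongest reply is that little of substance is lost. Several parts of it stand.

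- Overall subject incidence is hardly touched, by step 5. A reader might apply the formula of step 4 to overall incidence: with 50% true incidence and 20% vs 10% of subjects cut at day 7, it gives 41.0% vs 45.5%, an apparent excess of 4.5 points on ciNPT. That treats subjects with an SSC as having had no event before the cut, so it does not describe the group that the rule reaches.
- A reader might infer that a later death or readmission goes wholly unrecorded. The documents do not support that. Readmission, hospital and ICU days and relatedness to the revision are collected at all post-surgery visits (4.11.3), interventions for an SSC are documented (4.11.2), and the reason for discontinuation is recorded (4.16). What is lost is the adverse event or SAE report.
- A reader might infer that serious events after the switch cannot reach the sponsor's evaluation of unanticipated device effects (7.9). Related SAEs are kept. Only those judged unrelated drop out.
- A reader might take any new dressing as alternative therapy, because 4.10.3.3 records "Type of dressing (if any) applied after removal of study treatment". That section does not call the dressing a therapy, and this reading would also remove every such subject from the modified per-protocol set. The fair criticism is that the term is undefined.
- Safety analysis is mainly descriptive (SAP 9), the safety endpoint states no 90-day window, and subjects withdrawn under 4.15 lose data under 4.4.2 whatever 7.7 says.

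None of this reconciles 7.7 with the visit schedule, the SAP event window or the death listings. An event that was never reported as such may not be recoverable at analysis.

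**Conclusion.** The contradiction is in the current text and should be fixed. Protocol 7.7 cuts event reporting for subjects who are still being seen, mainly those with an SSC, and filters their later SAEs through an unblinded relatedness judgement. Under the assumptions of step 3, about 2.5% to 18.4% of 90-day event follow-up is lost on standard of care and 1.3% to 9.2% on ciNPT. The upper end needs every subject with an SSC to switch at day 7 and stay to day 90, so it is a ceiling for that group. Actual size and direction depend on how often alternative therapy is used in each arm, which the documents do not give.

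The damage is to later events by preferred term, seriousness and severity, and to the death listing. SSC assessment continues regardless, so the primary endpoint is not affected.

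**What to change.** In Protocol 7.7, delete the clause that ends reporting at alternative therapy and the sentence that restricts later SAEs to related ones. State that all adverse events and SAEs are reported from randomization to the Long Term Follow-up visit or study withdrawal, whichever comes first. Define alternative therapy for reporting and analysis, say how it relates to the cross-over therapy of 4.15, and record its start date. In SAP 9.1, keep the all-study treatment-emergent table as the main one and add one table of events with onset before alternative therapy. If any subjects have already been cut off under the current rule, give their number by arm in the study report.

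The cost is a protocol wording change, one date field, one extra table and slightly more data entry. The visits and assessments already exist. The change does not recover data from subjects withdrawn under 4.15 and 4.4.2, and the report should say so.
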